**Safety assessment parameters**

|                                  |  |
|----------------------------------|--|
|                                  | 
Safety evaluation is based on the following parameters (between V1 and V3) compared between therapy and placebo groups.
 
Frequency of adverse events (AEs) and/or serious adverse events (SAEs) in the treatment groups, including:
 
 
- Overall AE rate as compared to placebo;
 
- Frequency of AEs according to the results of physical examinations during each visit compared with placebo;
 
- AE incidence according to the results of the vital signs assessment (HR, BP, BT, RR) at each visit in comparison with placebo;
 
- AE incidence according to the ECG results on Day 15 (<math>\pm 2</math>) in comparison with placebo;
 
- Frequency of AEs incidence according to the results of laboratory examinations on Days 7(<math>\pm 2</math>) and 15(<math>\pm 2</math>) compared with placebo;
 
- Frequency of AEs according to the patients' records in the diary
 
 
Diary records will be reviewed by the Investigator and for those records presumed to meet criteria of an AE, the patient will be questioned. If the investigator judges that the AE criteria have been met, all information relevant for an AE (including an evaluation of causality to the investigational product) will be documented.
 
The AEs will be described according to the scheme given below:
 
 
- AE description;
 
- AE severity;
 
- AE duration;
 
- Causal relationship with the investigational product;
 
- Outcome.
 
 
All AEs will be coded according to MedDRA terms.
 |
| 
Inclusion Criteria
 | 
Patients will be considered eligible if they meet the following inclusion criteria:
   |

|  |  |
|--|--|

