| 
Statistical Analysis
 | 
The aim of the statistical analysis will be to prove the efficacy and safety of LRG-002 (Lactobacillus rhamnosus GG not less than <math>2 \times 10^{10}</math> CFU) to be superior to placebo in antibiotic-treated patients with acute respiratory diseases, as an adjunct treatment for prophylaxis of antibiotic-associated diarrhea (AAD).
 
The analysis will be performed for comparison of:
 
 
- LRG-002 and matching placebo.
 
 
The primary efficacy endpoint will be analyzed with a logistic regression model with fixed factors for treatment group and age group.
 
The primary efficacy endpoint will be considered achieved if the odds ratio for the occurrence of AAD between placebo and LRG-002 is significantly higher than 1 (i.e. the occurrence of AAD is lower in the LRG-002 group).
 
The secondary parameters will be compared with the following method:
 
 
- continuous variables will be compared by Mann—Whitney-Wilcoxon test.
 
 
Binary and ordinal variables will be compared by chi- square test or Fisher's exact test (depending on the number of expected observations per cell: <math><5</math> or <math>\geq 5</math>).
 
The analysis of study subjects with AE (SAE) will be performed with chi-square test or Fisher's exact test.
 
Poisson regression will be used for analysis of AE (SAE) frequency. The significance level is assumed as <math>p < \alpha</math>, with <math>\alpha = 0.05</math>.
 
Sample size calculation
 
Primary endpoint is the frequency of occurrence of AAD from the
 |

first to the last day of LRG-002 administration compared with placebo in antibiotic-treated patients with ARDs.

A test based on odd ratio was used to calculate sample size.

The following parameters were obtained from Figure 2 in a meta-analysis [1] using only data for AAD:

Using only data for AAD studies in adults from the cited publication, the rate for the control group is 0.24 and for the treatment group 0.14.

Using only data for LGG studies in adults and children, the rate for the control group is 0.26 and for the treatment group 0.15.

In meta-analysis [14] figures from Table 1 demonstrate a rate of 0.196 for a treatment group and 0.29 for a placebo group (only trials for adults with LGG were taken into consideration).

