### **9.3 Requirements for reports, procedures on recording and reporting of adverse events and intercurrent diseases**

#### **9.3.1 Terminology of adverse events and serious adverse events**

**Adverse event (AE)** — any medically unfavorable event identified in a patient or subject in a clinical trial after the use of medicinal product, which may not have a causal relationship with its use.

Thus, an adverse event (AE) may be any adverse and undesirable clinical sign (including laboratory deviation from the norm), symptom or disease, the time of occurrence of which does not exclude a causal relationship with the use of the drug, regardless of the presence or absence of such a relationship.

**Serious adverse event (SAE)** — any adverse medical event that regardless of the dose of the medicinal product:

- causes fatal outcome;
- is life threatening;
- requires hospitalization or its extension;
- results in persistent or significant disability/incapacity;
- is a congenital anomaly or malformation;
- is clinically relevant: the decision about whether the express reporting is appropriate in other situations (e.g., in cases of medically important events that do not pose an immediate threat to the patient's life, do not result in death or hospitalization, but put the patient at risk or require intervention to prevent one of the above outcomes given in the definition) is made on the basis of a medical and scientific assessment. Such cases should also be considered as serious adverse events.

These characteristics / consequences must be considered at the time of event occurrence. For example, the concept of life-threatening AE refers to a medical event in which a subject is at risk of death at the time of the AE development; it does not refer to a medical event that could hypothetically cause death in case of a higher severity condition.

**(Serious) adverse reaction ((S)AR)** — any (S)AE for which there is a reasonable probability of a causal relationship with the use of the medicinal product in the opinion of the Investigator or Sponsor (see paragraph 8.8.3 below).

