Patient complaints based on the results of the daily records of well-being self-assessment in the diary will be summarized into groups, and comparison between groups shall be made using appropriate tests for quantitative and qualitative data. Gastrointestinal AEs (determined using standardized MedDRA requests for the corresponding symptoms), regarded by the Investigator as associated with the study therapy, will be analyzed separately. Descriptive statistics methods will be used for the results. Comparison of the incidence of new AEs in the study groups will be carried out using the Fisher's exact test or the chi-square criterion, depending on the number of prospective observations in one cell ( $<5$  or  $\geq 5$ ); the comparison of severity degree (and possible causal relationship between received medicinal product and AE) will be carried out using the Cochran – Armitage test for linear trends for ordered categorical data.

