7.1. Primary endpoint analysis

Assessment of the incidence of AAD from Day 1 to the last day of the course of LRG-002 use vs. placebo in ARD patients receiving standard antimicrobial therapy. The primary efficacy criterion will be considered met if the odds ratio for AAD between the two groups is statistically significantly greater than 1 (i.e., the incidence of AAD in the LRG-002 group is lower than in the placebo group).

STATISTICAL ANALYSIS PLAN

The primary efficacy endpoint will be analyzed using a fixed-factor logistic regression model for the treatment group and age group. The treatment effect will be displayed using the adjusted odds ratio and the corresponding two-sided 95% confidence interval.

PCT will be calculated using the following set of functions of the R language:

- `glm` – building a logistic regression model;
- `summary` – displays the regression coefficients with an indication of the statistical significance;
- `confint` – displays confidence intervals for regression coefficients.

An example of a planned way of using these functions is shown in Figure 2. In the figure, the *Outcome* variable encodes the outcome (AAD – yes/no), *Treatment* encodes belonging to a particular study group, the *Age* variable encodes the age category (over or under 50 years old). The *p*-value is highlighted in red, the two-sided confidence interval is highlighted in blue, according to which the decision on reaching the PCT will be made.

```
> model_out <- glm(Outcome ~ Treatment + Age, data = df, family = "binomial")
> summary (model_out)
Call:
glm(formula = Outcome ~ Treatment + Age, family = "binomial", data = df)
Deviance Residuals:
    Min       1Q   Median       3Q      Max
-0.3327 -0.3327 -0.1635 -0.1635  2.9402

Coefficients:
            Estimate Std. Error z value Pr(>|z|)
(Intercept)  -4.3090    0.5949  -7.243 4.4e-13***
Treatment2    1.4427    0.6520   2.213 0.0269*
Ageage >=50  -0.5368    0.6558  -0.819 0.4130
```

```
Signif. codes: 0 '****' 0.001 '**' 0.01 '*' 0.05 '.' 0.1 ' ' 1

(Dispersion parameter for binomial family taken to be 1)

Null deviance: 135.35 on 509 degrees of freedom Residual deviance: 128.52 on
507 degrees of freedom
AIC: 134.52

Number of Fisher Scoring iterations: 7

> confint(model_out)
Waiting for profiling to be done...
      2.5%      97.5%
(Intercept) -5.7259968 -3.3150721
Treatment2  0.2808742  2.9311963
Age >=50    -2.0306660  0.6338301
```

Figure 2. Running functions for calculating PCT

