7.2. Analysis of secondary endpoints

The whole secondary efficiency analysis will be considered investigational, therefore multiplicity correction will not be performed; for test results, no formal capacity calculation will be provided.

Secondary efficiency points are classified into three groups:

1. Points characterizing the likelihood of a particular clinically significant event:
 - The occurrence rate of any diarrhea in the treatment group as compared to the placebo group;
 - The occurrence rate of C. difficile-associated AAD in the treatment group as compared to the placebo group;
 - The incidence of AAD not associated with C. difficile in the treatment group as compared to the placebo group;

- Frequency of gastrointestinal symptoms, including nausea, vomiting, flatulence, abdominal pain, and decreased appetite (according to the diary data), in the treatment group as compared to the placebo group;
- Number (share) of patients using standard symptomatic therapy to relieve symptoms of acute diarrhea in the treatment group as compared to the placebo group;
- The hospitalization rate in the treatment group as compared to the placebo group.

For these types of BKT, contingency tables 2×2 will be generated where the rows will show the groups, the columns will show the facts of the presence or absence of a particular event, the elements of the table are the patients included in the analysis. The contingency table data will be analyzed using Fisher's test (using the `fisher.test` function) or the chi-square test (using the `chisq.test` function) depending on the number of observations per cell (< 5 or ≥ 5).

2. Points characterizing the severity (or duration) of a particular clinical manifestation:

- Occurrence of bowel movements per day (according to the diary data) in the treatment group as compared to the placebo group;
- Duration of AAD (the time from the onset of AAD to the normalization of stool form according to BSS (types 1, 2, 3, and 4) and the presence of normal stool within 48 hours)) in the treatment group as compared to the placebo group;
- Duration of any diarrhea (time from diarrhea onset to normalization of stool form according to BSS (type 1, 2, 3, and 4) and presence of normal stool for 48 hours) in the treatment group as compared to the placebo group;
- Severity of the gastrointestinal symptoms, including nausea, vomiting, flatulence, abdominal pain, and decreased appetite (according to the diary data);

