8.1. Adverse events

Safety assessment will also be based on the following parameters (between Visits 1 and 3) compared between the investigational medicinal product and placebo:

Incidence of adverse events (AEs) and/or serious adverse events (SAEs) in the treatment groups including:

- Overall AE rate as compared to placebo;
- AE rate according to the results of physical examinations during each visit compared with placebo;
- AE incidence according to the assessment of the vital signs (HR, BP, BT, RR) at each visit as compared to placebo;
- AE incidence according to the ECG results on Day 15 (± 2) in comparison with placebo;
- AE incidence according to the results of laboratory examinations on Days 7 (± 2) and 15 (± 2) as compared to placebo;
- AE incidence according to the results of daily self-examination of the state of health recorded in Self-Observation Diary.

The study doctor will review the entries in the Self-Observation Diary. If the study doctor believes that the information in the Diary complies with the AE criteria, they will ask the patient about this event and document all information about the AE (including the causality assessment).

The AEs will be described according to the scheme given below:

- AE description
- Severity of the adverse event (meeting the severity criteria)
- AE severity
- AE duration
- Relation to the IMP
- Measures taken in relation to the investigational medicinal product
- Measures taken in relation to the patient

- **Outcome**

Adverse events will be coded according to the MedDRA

Methods of descriptive statistics will be used to represent the results. A comparison of the incidence of new AE cases in the study groups will be performed using the Fisher's exact test or the chi-square test, depending on the number of proposed observations in one cell (< 5 or ≥ 5), and a comparison of the severity (and the possible causality between the administered medicinal product and AE) will be conducted using the Cochran–Armitage test for linear trends for ordered categorical data.

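### The overall and diary-based AE comparisons partly re-measure the efficacy endpoints, because diarrhea and the diary GI symptoms also meet the AE definition and nothing separates them

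*SAP*

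**What the plan says.** **Efficacy side.** SAP 7.1 defines the primary endpoint as "Assessment of the incidence of AAD from Day 1 to the last day of the course of LRG-002 use vs. placebo in ARD patients" on standard antimicrobial therapy. SAP 7.2 lists as secondary endpoints "The occurrence rate of any diarrhea in the treatment group as compared to the placebo group", and the frequency and severity of nausea, vomiting, flatulence, abdominal pain and decreased appetite from the diary.

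**Safety side.** Protocol 9.3.1 lets an AE be "any adverse and undesirable clinical sign (including laboratory deviation from the norm), symptom or disease", whether or not it is related to the product. Protocol 9.3.4 has every AE from consent to the last visit documented. The diary is a source: the synopsis (Safety assessment parameters) says that "for those records presumed to meet criteria of an AE, the patient will be questioned", and the event is documented if the investigator judges the AE criteria met. In Appendix 3 the structured symptom items are stool time and type, temperature, and the same five GI symptoms.

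**Comparison.** SAP 8.1 lists "Overall AE rate as compared to placebo" and, separately, diary-based AE incidence, tested by Fisher's exact or chi-square test. Protocol 10.1.4 counts AEs regardless of association to treatment. The only GI-specific AE analysis is in protocol 10.1.4. It covers GI AEs "regarded by the Investigator as associated with the study therapy, will be analyzed separately", and SAP 8.1 does not repeat it.

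**Stated aim.** The synopsis (Statistical Analysis) says: "The aim of the statistical analysis will be to prove the efficacy and safety of LRG-002", and goes on to say superior to placebo.

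**The concern.** The same diary entries feed both sides of the benefit-risk assessment. If LRG-002 prevents diarrhea, patients spared an AAD are also spared an AE, so the overall AE rate falls for that reason alone. Set beside a synopsis aim that joins safety to superiority, the fall could be read as a second, separate finding. In the other direction, a rise in other AEs on LRG-002 could be offset in the same row by the fall in diarrhea.

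The related-GI analysis does not separate the two. AAD is defined as diarrhea associated with antibiotic use, and protocol 9.3.3 classes an event as not suspected when another medicinal product sufficiently explains it. An AAD entered as an AE would normally stay in the all-cause rate and fall outside that subset.

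**Working it through.** **Inputs.** AAD 0.26 on placebo and 0.15 on LRG-002, two-sided alpha 0.05, power 80%, 1:1 allocation, 20% withdrawal, 260 randomized per group (SAP 2.3). The safety population is all randomized and dosed patients (SAP 4.2.1), so up to 260 per group.

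**The plan's own figure.** ((1.96 + 0.8416)/(0.15 − 0.26))² × [0.15×0.85 + 0.26×0.74] = 648.7 × 0.3199 = 207.5, rounded up to 208. Then 208/0.80 = 260 per group and 520 in total. The plan's figures reproduce.

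**Assumptions not in the documents.** b is the share of patients with at least one other AE. It is independent of AAD and, at first, equal in both arms. q is the share of AADs entered as AEs. No AE rate is given, so a range of b is shown.

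**Overall AE rate per arm** = 1 − (1 − b)(1 − q × AAD rate). For b = 20%, q = 1:
- placebo: 1 − 0.80×0.74 = 40.8%
- LRG-002: 1 − 0.80×0.85 = 32.0%

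**Chance of p < 0.05** = Φ((d − 1.96·se₀)/se₁), where d is the difference, se₀ the pooled and se₁ the unpooled standard error with 260 per arm. For the same case d = 0.088, se₀ = 0.0422 and se₁ = 0.0420, giving Φ(0.126) = 55%.

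| Other AEs (b) | q = 1: placebo vs LRG-002 | Chance of significant advantage | q = 0.5: placebo vs LRG-002 | Chance |
|---|---|---|---|---|
| 10% | 33.4% vs 23.5% | 71% | 21.7% vs 16.8% | 30% |
| 20% | 40.8% vs 32.0% | 55% | 30.4% vs 26.0% | 20% |
| 30% | 48.2% vs 40.5% | 42% | 39.1% vs 35.3% | 15% |
| 50% | 63.0% vs 57.5% | 25% | 56.5% vs 53.8% | 9% |

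With AAD left out of the comparison, the chance is the nominal 5%, about 2.5% in each direction.

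**Offset harm.** Let other AEs be 20% on placebo and 30% on LRG-002, with q = 1.
- Overall: placebo 1 − 0.80×0.74 = 40.8%; LRG-002 1 − 0.70×0.85 = 40.5%. The chance of p < 0.05 is about 5%, which is chance level.
- Without AAD: 20% vs 30%, Φ((0.10 − 1.96×0.0380)/0.0377) = about 75%.
- With q = 0.5: 1 − 0.80×0.87 = 30.4% vs 1 − 0.70×0.925 = 35.3%, detected about 22% of the time, so the excess is diluted but not cancelled.

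Only AAD is modelled. The five diary symptoms could add to the effect in either direction.

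**The case against.** Four objections carry weight.

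**Entry as an AE is a judgement.** Diary entries become AEs only if the investigator finds the criteria met, and diarrhea has its own AAD/non-AAD assessment at each visit. A reader might infer that every AAD patient is counted as an AE patient. The documents do not say so, and the q = 1 column is the upper end. This stands. But no rule settles the matter either, so practice may differ across up to 40 sites.

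**Other displays exist.** A reader might infer that the plan hides harm throughout its safety analysis. It does not. Protocol 10.1.4 presents AEs by SOC and PT, and SAP Appendix 1 Tables 5 and 6 have those rows with p-values. Protocol 10.1.4 also gives the incidence of related or possibly related AEs, which should be largely free of AAD, and of AEs leading to discontinuation. AEs from physical examination, vital signs, ECG and laboratory results are compared separately. Offsetting is limited to the overall and diary-based rows. What these displays lack is a patient-level rate without diarrhea. PT rows cannot be subtracted to get it, because one patient may have several AEs.

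**There is no formal safety-superiority test.** A reader might take the 55% as the chance of a false safety claim. The objectives are to evaluate or investigate safety (protocol 4.2, SAP 2.1), and the only success criterion is the AAD odds ratio. The percentages are chances of a nominal p-value in a supportive table. The synopsis sentence still invites the wrong reading.

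**Diarrhea may be a product effect.** The protocol's own summary of a safety study in elderly volunteers lists diarrhea among expected AEs on LGG (section 3.3.2.1, Table 3). Replacing the all-cause rate with one that excludes diarrhea could move such an effect out of view. This stands, and it is why the excluded rates should sit beside the all-cause rate and not replace it.

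**Conclusion.** The point holds for the overall and diary-based AE comparisons. The overlap is documentary: the same events are efficacy endpoints and meet the AE definition, with no carve-out. Those rows are therefore not independent evidence on safety.

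The size is conditional on the planned AAD rates, 260 per arm, independence of AAD and other AEs, an assumed other-AE rate, and the share of AADs entered as AEs. Across the cases shown, the chance of a nominal AE advantage with no difference in other AEs runs from about 9% to 71%, against about 2.5% in that direction without the overlap. Complete cancellation of a 20% vs 30% excess needs full entry of AADs and an excess of about that size. Data collection, the primary analysis and the sample size are unaffected. This is a cheap improvement, best made before unblinding, since the same split made afterwards would look post hoc.

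**What to change.** Keep the all-cause AE comparison and all AE and SAE recording as planned. Then:

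1. In SAP 8.1 and protocol 10.1.4, prespecify beside the all-cause rate the share of patients with at least one AE other than diary-defined diarrhea (AAD or any diarrhea).
2. Give the same share with the five diary GI symptoms also excluded.
3. Show GI AEs as their own line by arm regardless of causality, in addition to the related-GI analysis.
4. In the synopsis (Statistical Analysis), limit the word superior to efficacy.

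The cost is a few extra table rows and some SAP and protocol wording. No new data are needed.

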### 9.3.2 Severity of adverse events

The term "severity" in this context describes the intensity of a particular event. It is necessary to distinguish it from the term "seriousness". In the course of the study, the Investigator should identify any AEs manifested and assess their severity as follows:

- Mild: commonly transient in nature AE, as a rule, not disrupting the usual daily activity.
- Medium: accompanied by significant discomfort that disrupts normal daily activity.
- Severe: interferes with normal daily activities.

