Appendix 1. Table layouts

Table No. 1. Example of a statistical table for a quantitative variable

Visit	Group	Parameter	Variable name
Visit number	Group 1	N	
		Missed	
		Mean	
		95% CI	
		SD	
		Median	
		Min	
		Max	
		Q1	
		Q3	
	IQR		
	Group 2	N	
		Missed	

STATISTICAL ANALYSIS PLAN

Visit	Group	Parameter	Variable name
		Mean	
		95% CI	
		SD	
		Median	
		Min	
		Max	
		Q1	
		Q3	
		IQR	

Table No. 2. Example of a group comparison table for a quantitative variable

Visit	No.	No.	No.	No.
Variable	variable name			

STATISTICAL ANALYSIS PLAN

Shapiro–Wilk test, p-value	Group 1				
	Group 2				
Student's t-test, p-value					
Mann–Whitney test, p-value					

Table No. 3. Example of a repeated comparison table for a quantitative variable

Variable	Group	Visit	Friedman test/ ANOVA for repeated measurements	Wilcoxon test/ Student's t-test for repeated measurements
variable name	Group 1	Comparison of visits		
		No. vs. No.		

STATISTICAL ANALYSIS PLAN

Variable	Group	Visit	Friedman test/ ANOVA for repeated measurements	Wilcoxon test/ Student's t-test for repeated measurements
		No. vs. No.		
		No. vs. No.		
		No. vs. No.		
		No. vs. No.		
		No. vs. No.		
	Group 2	Comparison of visits		
		No. vs. No.		
		No. vs. No.		
		No. vs. No.		
		No. vs. No.		

STATISTICAL ANALYSIS PLAN

Variable	Group	Visit	Friedman test/ ANOVA for repeated measurements	Wilcoxon test/ Student's t-test for repeated measurements
		No. vs. No.		
		No. vs. No.		

Table No. 4. Example of a statistical table for a categorical variable

Variable	Visit	Group	Variable value	Amount	% by group	% by groups for visit	Fisher's test, p-value
variable name	No.	Group 1	value				
			value				
		Group 2	value				
			value				

STATISTICAL ANALYSIS PLAN

Table No. 5. Example of a table of adverse events for calculating the number of all adverse events

Adverse events	Group	Amount	% of the number of AEs in the group	% of the total number of AEs	Binomial test, p-value
All adverse events	Group 1				
	Group 2				
SOC	Group 1				
	Group 2				
PT	Group 1				
	Group 2				

Table No. 6. Example of a table of adverse events for calculating the number of adverse events in the context

Adverse events	Group	variable name	Amount	% of the number of AEs in the group	% of the total number of AEs	Fisher's test, p-value
	Group 1	value				
		value				

STATISTICAL ANALYSIS PLAN

Adverse events	Group	Variable name	Amount	% of the number of AEs in the group	% of the total number of AEs	Fisher's test, p-value

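### AE severity and causality are compared by a trend test with no stated unit or denominator; run on AE records, as the plan implies, that p-value can miss or reverse added harm

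*SAP*

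**What the plan says.** SAP 8.1 gives the severity and causality comparison in one clause: "a comparison of the severity (and the possible causality between the administered medicinal product and AE) will be conducted using the Cochran–Armitage test". Protocol 10.1.4 has the counterpart: "the comparison of severity degree (and possible causal relationship between received medicinal product and AE) will be carried out using the Cochran"–Armitage test. Neither text says whether the unit is the AE or the patient, which denominator applies, or which scores are used.

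Three other places bear on the unit:

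- Protocol 9.3.2 makes severity a property of an event: "the Investigator should identify any AEs manifested and assess their severity as follows", followed by mild, medium and severe. There is no level for a patient without an AE. Causality (protocol 9.3.3) is likewise judged per AE, as suspected or not suspected.
- SAP Appendix 1, Table 6 is titled "Example of a table of adverse events for calculating the number of adverse events in the context". Tables 5 and 6 both give percentages "of the number of AEs in the group" and of all AEs. Neither has a safety-population denominator.
- Table 6 heads its p-value column with Fisher's test, and Table 5 with a binomial test. Neither names the trend test in the text.

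The plan also compares occurrence. The sentence in SAP 8.1 that contains the severity clause opens with "A comparison of the incidence of new AE cases in the study groups will be performed using the Fisher's exact test or the chi-square test", and the list above it includes "Overall AE rate as compared to placebo".

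**The concern.** A severity comparison restricted to AE records conditions on something that happens after randomisation and that treatment may change. Its null hypothesis is that the mix of grades among AEs is the same in both arms. That differs from asking whether patients on LRG-002 have more, or more severe, AEs than patients on placebo.

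Three consequences follow. If LRG-002 multiplied every grade by the same factor, the mix would be unchanged and the test would have nothing to detect. If LRG-002 added only mild AEs, the average grade among its AEs would fall, and the test would move in its favour. If patients contribute several AEs, the records are not independent, as the test requires.

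The second case is relevant here. The protocol describes the known reactions as mild gastrointestinal complaints (section 3.1.1, Adverse Reactions), and the synopsis aims to show efficacy and safety superior to placebo. A significant shift towards milder AEs could be read as support for that aim when it came from extra AEs.

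**Working it through.** **Arm size.** The plan gives no AE rate, grade distribution or power for this test, so there is no stated AE figure to reproduce. The arm size does reproduce: (1.960 + 0.842)² × [0.15×0.85 + 0.26×0.74] / 0.11² = 207.5, rounded up to 208; 208/0.80 = 260 per arm, 520 in total. Arms of 260 are used below. **All AE counts and rates below are assumptions.**

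**Statistic.** With scores s, Z = (mean score on LRG-002 − mean score on placebo) / √[V(1/n₁ + 1/n₂)], where V is the pooled variance of the scores. AE records only: s = 1, 2, 3 and n is the number of AEs. All patients: s = 0 for no AE, then 1, 2, 3, and n = 260. The examples have one AE per affected patient.

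**Only mild AEs added** (mild/medium/severe 60/15/5 on LRG-002, 20/15/5 on placebo):

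- AE records: means 105/80 = 1.3125 and 65/40 = 1.625. V = 290/120 − (170/120)² = 0.4097. Z = −0.3125/√(0.4097 × 0.0375) = −2.52, p = 0.012, **in favour of LRG-002**.
- All patients: means 105/260 = 0.404 and 65/260 = 0.250. V = 290/520 − (170/520)² = 0.4508. Z = 0.1538/√(0.4508 × 2/260) = +2.61, p = 0.009, **against LRG-002**.
- Incidence, 80/260 against 40/260: chi-square p = 0.00003, against LRG-002.

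With a smaller excess (40/15/5 against 20/15/5) the AE-record test gives Z = −1.52, p = 0.13, and incidence gives p = 0.026.

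**Every grade doubled** (40/30/10 against 20/15/5):

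- AE records: both means are 1.625, so Z = 0 and p = 1.
- All patients: means 0.500 and 0.250. V = 375/520 − (195/520)² = 0.5805. Z = +3.74, p = 0.0002.
- Incidence: p = 0.00003. At lower rates the incidence test weakens: 30 against 15 patients gives p = 0.019 (Fisher 0.028); 16 against 8 gives p = 0.094 (Fisher 0.14).

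**Repeated trials.** Simulation with 260 per arm, one AE per affected patient, placebo 12% mild, 6% medium, 2% severe, two-sided 5%, incidence taken per patient:

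| Change on LRG-002 | AE-record trend significant in favour of LRG-002 | Incidence test against | Worst-grade trend against | Favourable trend with no incidence signal |
|---|---|---|---|---|
| +5 points mild | 12–14% | 28% | 13% | 9–10% |
| +12 points mild | about 40% | 88% | 52% | about 5% |
| +20 points mild | 69% | 99.9% | not needed here | about 0.1% or less |
| every grade doubled | about 5% in either direction | over 99% | 99% | – |

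With no difference, the AE-record and worst-grade trend tests each reject in about 5%, and a favourable severity result with no incidence signal occurs in about 2.4%. At 208 per arm the 40% becomes 33%.

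**Repeat AEs.** If each affected patient has m AEs with within-patient grade correlation ρ, the variance is inflated by about 1 + (m − 1)ρ, and the actual error rate is 2Φ(−1.96/√[1 + (m − 1)ρ]). For m = 2, ρ = 0.3: inflation 1.3, error 8.6%. For m = 3, ρ = 0.8: inflation 2.6, error 22%. Simulation with 2 to 3 correlated AEs per affected patient gave roughly 9–25%; the worst-grade test stayed at 4–6%. Several AEs per person are plausible: the study in healthy elderly volunteers summarised in the protocol had 47 AEs in 15 people (47/15 = 3.1), although over a longer follow-up than here.

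**The case against.** **The AE-record reading is inferred.** This is correct. No sentence says that the trend test is confined to AEs, and Table 6, the closest shell, names Fisher's test. A reader might infer that the plan prescribes an AE-only test; it does not. It leaves the unit open, and every stated element (grade scale, causality scale, table denominators) points to AE records. If patients were intended, the text still has to say so.

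**Other analyses look at the same harm.** This also stands. SAP 8.1 compares AE incidence, and the protocol synopsis specifies chi-square or Fisher for subjects with an AE and Poisson regression for AE frequency. SAP 7.2 compares nausea, vomiting, flatulence, abdominal pain and decreased appetite in 2×2 tables of patients. Protocol 10.1.4 determines the incidence of related or possibly related AEs and analyses treatment-related gastrointestinal AEs separately. It is tempting to conclude that a doubling of AEs would go unseen, or that extra mild harm would pass as better safety overall. The documents do not support that.

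**The incidence test beats the worst-grade test for a mild excess.** True: 88% against 52% at 12 points. The worst-grade test replaces the severity comparison; it does not replace incidence.

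**The rates are chosen.** True. The protocol calls adverse reactions to probiotics extremely rare, so a 12- to 20-point excess is a stress case. The direction of the effects does not depend on the rates; the percentages do.

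**Conclusion.** The concern holds for the severity and causality comparison in SAP 8.1 and protocol 10.1.4, and for that comparison only. Unit and denominator are missing, and the implied test on AE records answers a question conditional on having an AE. It gives Z = 0 for a proportional rise in all grades, shifts towards LRG-002 when mild AEs are added (about 40% of trials significant at 12 extra points under the assumed rates), and has an error rate of roughly 9–25% with 2 to 3 correlated AEs per affected patient.

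The incidence comparison limits the damage. A favourable severity result with no incidence signal remains in about 5% of the 12-point trials and 9–10% of the 5-point trials. More often the report would carry two p-values pointing in opposite directions, with no stated rule for reading them together. Because a standard per-patient version exists at almost no cost, the comparison should be changed and not merely clarified. It does not affect the primary endpoint or the sample size.

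**What to change.** In SAP 8.1 and protocol 10.1.4:

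1. Apply the trend test to one value per safety-population patient, the worst AE grade: 0 no AE, 1 mild, 2 medium, 3 severe. State these scores.
2. For causality, compare the proportion of safety-population patients with at least one AE judged suspected, by chi-square or Fisher.
3. Keep the AE incidence comparison and state that the severity result is read beside it.
4. In Table 6, add the number and percentage of safety-population patients by worst grade, and align the p-value heading with the test named in the text.
5. Keep the mix of grades among AEs as description, without a p-value.

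The cost is a change of wording in two documents, one derived variable, and additional table columns. No new data or visits are needed. There are two downsides. Repeat AEs within a patient leave the test, although they stay in the descriptive tables. For a purely mild excess the worst-grade test is less sensitive than the incidence test, which is why the latter must be kept.
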